Protocol Description: **This cluster-randomized trial will compare changes in attitudes and knowledge on administering naloxone based on exposure to either a virtual reality educational training or the current standard educational trainings (e.g. on-line videos, printed information handouts) offered at local libraries. Individuals attending local library's naloxone training days will voluntarily complete an anonymous validated survey pre and post attending either the virtual reality or standard educational training.**
Application Type: **EXEMPT Category 1**

Resubmission*

No

Study Personnel

Principal Investigator

Name: **[name]**
Dept / School / Div: **602 - Biobehavioral and Health Sciences**
Campus Address
Mail Code
Address: **[name]**
City State Zip: **-**
Phone:
Fax:
Pager:
Email: **Yes**
HS Training Completed: **03/04/2022**
Training Expiration Date: **CITI Protection of Human Subjects Research Training - ORA**
Name of course completed :

products, tissues or body fluids)?

No

Medical Information Disclosure*

Does the research proposal involve the use and disclosure of research subject's medical information for research purposes?

No

If the answer is YES, indicate which items is is provided with this submission:

CTRC Resources*

Does the research involve CTRC resources?

No

Pathology and Laboratory Medicine Resources*

Will samples be collected by hospital phlebotomy and/or processed or analyzed by any of the clinical laboratories of the University of Pennsylvania Health System?

No

Research Involves Apheresis, Cell Collection, and/or Blood Product Collection*

Does this research involve collection of blood products in the Penn Donor Center and/or the use of apheresis for treatment or collection of cells or other blood components?

No

Research involving blood transfusion or drug infusions*

Will your research involve blood transfusion or infusion of study drug in 3 Ravdin Apheresis Unit for research purposes?

No

Trial in Radiation Oncology

Is this research a prospective trial being done in Radiation Oncology, and if so, has this protocol been approved by the Radiation Oncology Protocol committee?

N/A

Study in Radiation Oncology

Is this research a retrospective study being done in Radiation Oncology, and if so, has this project been reviewed by the Radiation Oncology Clinical Research Group?

N/A

Use of UPHS services*

Does your study require the use of University of Pennsylvania Health System (UPHS) services, tests or procedures*, whether considered routine care or strictly for research purposes?

No

Primary Focus*

Survey research (the main focus of the research is administration of a survey to research subjects)

Protocol Interventions

	Sociobehavioral (i.e. cognitive or behavioral therapy)
	Drug
	Device - therapeutic
	Device - diagnostic (assessing a device for sensitivity or specificity in disease diagnosis)
	Surgical
	Diagnostic test/procedure (research-related diagnostic test or procedure)
	Obtaining human tissue for basic research or biospecimen bank
	Survey instrument
	None of the above

The following documents are currently attached to this item:

There are no documents attached for this item.

Sponsors

Business Administrator

Name:	[name]
Dept / School / Div:	602 - Biobehavioral and Health Sciences
Phone:	-
Fax:	-
Pager:	
Email:	

Department budget code

000 - 000 - 0 - 000000 - 0000 - 0000 - 0000

Funding Sponsors

Funding sponsors billing address

If you have selected a commercial or industry sponsor, please provide the appropriate address and contact information for the Sponsor for the purposes of billing for IRB review fees (initial review, continuing review and convened modification fees apply here). If the Sponsor is not industry/commercial, this information is not necessary to provide with your application.

Funding sponsors gift

Is this research being funded by a philanthropic gift?

No

Project Funding*

Is this project funded by or associated with a grant or contract?

No

Sponsor Funding

Is this study funded by an industry sponsor?

Status of contract

The following documents are currently attached to this item:

Protocol

Objectives

Overall objectives

The central hypothesis is that immersive virtual reality opioid related overdose educational trainings will result in increased knowledge retention and comfort level to administer naloxone among community members voluntarily participating in in-person trainings at libraries.

Background

Since 2000, the United States has experienced a 200% increase in the rates of deaths by overdose that involve opioids, including opioid pain relievers and heroin. Since 2010, deaths from heroin overdose have more than tripled. In response to this epidemic of deaths by opioid overdose, the state of Pennsylvania, along with more than 40 other states in the nation, have enacted standing orders of Naloxone (Narcan®), a fast acting opiate antagonist. This means that Naloxone, which has been shown to prevent death by reversing opioid overdoses, is available for anyone, without a visit with a healthcare provider, to request and fill a prescription at local pharmacies. As the opioid overdose epidemic worsens, there is an urgent need to prepare individuals to be competent actors in cases of opioid overdoses. Providing access to optimal education on naloxone administration is an important intervention in the effort to reduce deaths by opioid overdose. Library patrons are uniquely positioned to reduce preventable overdose deaths in their communities if properly trained to know when and how to respond. Penn researchers recently developed a nurse led, evidence-based 9 minute virtual reality (VR) naloxone administration educational training. Preliminary results indicate that healthcare profession students participating in VR training at Penn preformed just as well as those who received in person high-tech, high-cost simulation training in regard to their knowledge and attitudes about administering naloxone. Compared to in-person trainings, VR offers an engaging informative naloxone training that requires less manpower and has fewer geographic or time constraints. Assuring optimal education to these key personnel is an important intervention in the fight to reduce deaths by opioid overdose. In September 2019, the Philadelphia Department of Public Health will offer "Narcan Handout Days" at libraries across the city. Health Department staff are present at libraries, sitting at display booths providing training materials and free naloxone kits to library patrons interested in learning more about how to help address the public health crisis. We want to leverage this unique opportunity occurring in September to evaluate the use of virtual reality to provide comprehensive opioid overdose education.

Study Design

Design

This study will utilize a cluster-randomized trial design. Entire libraries will be randomized to either offer community members the virtual reality training or the standard educational offerings (e.g. handouts, online videos). Volunteers will be asked to complete the brief, anonymous, and validated Opioid Overdose Knowledge Scale & Opioid Overdose Attitudes Scale prior to receiving an education intervention (pretest) and then again immediately after (posttest). Neither participants nor investigators will be blinded. Library patrons who do not participate in the study will be offered current standard training materials. Regardless of the library's randomization, to either virtual reality or standard training, all patrons completing pre and post test surveys will have the opportunity to view the virtual reality training or other public health department materials.

Study duration

The new project dates of the proposed study are September 2019-August 2020. This will enable enrollment to occur throughout September at "Naloxone Handout Days" as well as at once monthly trainings offered by the department of public health at the South Philadelphia Library for local community members to walk in.

Characteristics of the Study Population

Target population

Our target population includes library patrons voluntarily attending the department of public health's "naloxone handout days" and monthly educational trainings. This enrollment strategy across free libraries and zip codes will provide ample opportunities for local city residents living in diverse settings to attend and receive valuable opioid overdose education.

Subjects enrolled by Penn Researchers

125

Subjects enrolled by Collaborating Researchers

0

Vulnerable Populations

Children Form

Pregnant women (if the study procedures may affect the condition of the pregnant woman or fetus) Form

Fetuses and/or Neonates Form

Prisoners Form

Other

None of the above populations are included in the research study

The following documents are currently attached to this item:

There are no documents attached for this item.

Subject recruitment

The investigators and personnel listed on this study protocol will be present at each library sitting next to the Department of Public Health staff at a table in each library's lobby. For recruitment of library patrons in September 2019, the investigator or study personnel at the library site on "Naloxone Handout Days" will read a pre-developed script describing the study, explaining potential risks and benefits, and making clear that participation, choosing not to participate, or withdrawing from the study will not influence a patron's ability to use the library or department of public health's resources. This script will be used to guide a brief talk given by a study investigator. A large flyer will be posted next to the table promoting the Virtual reality training for individuals who are interested in learning more and talking to an investigator or study personnel about anonymously participating. Informed consent will be obtained via participants signing the first page before beginning the pre-test survey. After obtaining informed consent, respondents will be asked to complete the pretest baseline assessments. Participants can contact the PI to discuss the study at any time.

Will the recruitment plan propose to use any Penn media services (communications, marketing, etc.) for outreach via social media avenues (examples include: Facebook, Twitter, blogging, texting, etc.) or does the study team plan to directly use social media to recruit for the research?

No

The following documents are currently attached to this item:

There are no documents attached for this item.

Subject compensation*

Will subjects be financially compensated for their participation?

Yes

The following documents are currently attached to this item:

There are no documents attached for this item.

If there is subject compensation, provide the schedule for compensation per study visit or session and total amount for entire participation, either as text or separate document

None

Study Procedures

Suicidal Ideation and Behavior

Does this research qualify as a clinical investigation that will utilize a test article (ie- drug or biological) which may carry a potential for central nervous system (CNS) effect(s)?

No

Procedures

During the study period we will be committed to testing the 9 minute virtual reality training to review Naloxone administration and overdose management. The efficacy of this virtual reality education compared to standard educational materials (e.g. online videos, printed handouts) on knowledge retention and attitudes will be evaluated according to the study procedure schema (uploaded separately). As shown in the study procedure schema, all voluntary participants in both experimental and control libraries will complete informed consent documents, provide demographic data, and complete pretest Opioid Overdose Knowledge Scale & Opioid Overdose Attitudes Scale surveys via Qualtrics, a secure online survey system maintained by the University of Pennsylvania and stored behind firewall protected servers. No identifiers will be collected. The surveys are anonymous. Virtual Reality Education (Intervention): The experimental group of libraries will receive the virtual reality simulation, which is guided by the NLN Jeffries Simulation Theory, and lasts 9 minutes. The virtual reality education is based on scenes and dialogue conducted during the hybrid high-fidelity simulation, from a script developed using the existing hybrid simulation on opioid overdose intervention. This virtual reality education is an educational intervention. Standard Educational (Control): The public health department's training includes printed handouts on how to administer naloxone and youtube videos on how to spot signs and symptoms of overdose and administer naloxone. Additionally, staff are on hand to provide one on one verbal educational trainings to local community members voluntarily seeking education. All individuals approaching the table at the library will be introduced to the study and its purpose. If an individual attending the free training is interested in participating the study they will be consented by an investigator listed on this personnel. After consenting all individuals will be asked to complete a brief pre-survey. If the library is randomized to a virtual reality cluster, participants will be asked to view the educational training using provided virtual reality headsets. If the library is randomized to a control cluster the participants will be offered training materials provided by the health department (e.g. youtube videos, printed handouts, on narcan administration). All participants, regardless of cluster will be asked to complete the same survey immediately after either the virtual reality or public health department training. All individuals who participate in the study will have the opportunity to view the virtual reality training or public health department materials at any library regardless of cluster assignment following completion of post-test survey. Those who do not wish to participate in the study will have the opportunity to review the public health department's training materials.

The following documents are currently attached to this item:

There are no documents attached for this item.

Deception

Does your project use deception?

No

International Research

Are you conducting research outside of the United States?

No

Analysis Plan

Descriptive statistics will be calculated for the sample by cluster. Cohorts will be evaluated, pretest, for

differences in demographic characteristics using independent sample t-test, or chi-square test of proportions when appropriate. Similarly, independent t-test will assess differences in pre-test knowledge and attitudes prior to intervention between control and experimental groups, and again with a posttest analysis. Paired t-test will assess within cohort changes in knowledge and attitudes towards recognizing signs of overdose and intervening during an observed opioid related overdose in the community settings. Sample sizes of 30-50 participants, when sampling 6-10 libraries, or clusters, with an with an average of 5 subjects in each cluster, achieves 85% to 94% power to detect a difference in OOKS scores between the group means of at least 4 points using a two sided t-test at significance level of 0.05. The standard deviation of subjects is 5. The intracluster correlation coefficient is assumed to be 0.010. Structural equation modeling will assess differences in control and treatment participants post scores while adjusting for relevant covariates including baseline knowledge and attitudes.

The following documents are currently attached to this item:

There are no documents attached for this item.

Subject Confidentiality

Sources of research material will include data obtained from the Opioid Overdose Knowledge Scale and Opioid Overdose Attitude Scale surveys as well as demographic data. Data will be collected via an anonymous Qualtrics Surveys. Data will be managed by the Principal Investigator on the firewall protected Penn Nursing servers. The minimal risk associated with this study is the risk related to identity protection. Because this study requires measurement of pretest and posttest data, participants data must be matched. Therefore, participants will be given unique identification numbers to use in place of their names to mark their pre- and posttest surveys. In the event of the Qualtrics Survey not being accessible (e.g. wifi outage) hard copies of the survey will be made available. These hardcopies will be stored in a locked file to which only the PI and co-investigator will have access. All electronic and digital data will be stored on a secure survey at the University of Pennsylvania for two years, after which point the data will be destroyed. No identifiers are asked on the anonymous survey.

Sensitive Research Information*

Does this research involve collection of sensitive information about the subjects that should be excluded from the electronic medical record?

No

Data Disclosure

Will the data be disclosed to anyone who is not listed under Personnel?

No

Data Protection*

Name

Street address, city, county, precinct, zip code, and equivalent geocodes

All elements of dates (except year) for dates directly related to an individual and all ages over 89

Telephone and fax number

Electronic mail addresses

Social security numbers

Medical record numbers

Health plan ID numbers

Account numbers

Certificate/license numbers

Vehicle identifiers and serial numbers, including license plate numbers

Device identifiers/serial numbers

Web addresses (URLs)

Internet IP addresses

Biometric identifiers, incl. finger and voice prints

Full face photographic images and any comparable images

x Any other unique identifying number, characteristic, or code

None

Does your research request both a waiver of HIPAA authorization for collection of patient information and involve providing Protected Health Information ("PHI") that is classified as a "limited data set" (city/town/state/zip code, dates except year, ages less than 90 or aggregate report for over 90) to a recipient outside of the University of Pennsylvania covered entity?

No

Consent

1. Consent Process

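### Libraries are randomised, but neither between-arm efficacy analysis is stated to account for library; at the plan's own inputs the type I error is about 5.5% instead of 5%

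*Combined protocol and SAP*

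**What the plan says.** The Design section makes the library the unit of randomisation: "Entire libraries will be randomized to either offer community members the virtual reality training or the standard educational offerings".

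The Analysis Plan contains two between-arm efficacy analyses:
- a t-test: "independent t-test will assess differences in pre-test knowledge and attitudes prior to intervention between control and experimental groups, and again with a posttest analysis";
- an SEM: "Structural equation modeling will assess differences in control and treatment participants post scores while adjusting for relevant covariates including baseline knowledge and attitudes".

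Clustering is recognised in the sample-size statement, which reads "Sample sizes of 30-50 participants, when sampling 6-10 libraries, or clusters, with an with an average of 5 subjects in each cluster" and adds "The intracluster correlation coefficient is assumed to be 0.010". The only other mention in that section is "Descriptive statistics will be calculated for the sample by cluster". Even this may mean by arm, because the Procedures section uses the word for the arms as well: "If the library is randomized to a virtual reality cluster".

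On data collection, Subject Confidentiality says that "participants will be given unique identification numbers to use in place of their names to mark their pre- and posttest surveys". It does not mention a library code. The questionnaire is listed as an attachment but is not shown, so library may be on it.

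**The concern.** The trial is sized on the assumption that people at the same library resemble each other, but no efficacy analysis is stated to allow for this. A t-test that treats participants as independently randomised takes its standard error and its degrees of freedom from people, when the randomised units are libraries. Its p-values are then too small and its intervals too narrow, and a chance difference between a few libraries is more easily read as an effect of virtual reality.

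Two features of the plan could make this worse than the sample-size inputs suggest. The enrolment figure is 125, against 30 to 50 in the power statement, and the number of libraries supplying them is not given. Enrolment also continues monthly at one named library until August 2020. Under library randomisation all of those participants fall in one arm, so that library's own character is mixed with the treatment effect.

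The pretest comparisons between arms are not part of this point.

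**Working it through.** **Inputs from the documents.** Difference 4 OOKS points, SD 5, ICC 0.010, average 5 per library, two-sided 5% level, 30 to 50 participants in 6 to 10 libraries (Analysis Plan); enrolment 125 (Characteristics of the Study Population). **Assumptions.** Pre-post correlation 0.5 unless stated; ICC 0.05 as a sensitivity value; 60 of 125 participants from one library as an uneven case.

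**1. The plan's own power figure (85% to 94%).** The design effect is DE = 1 + (m − 1) × ICC = 1 + 4 × 0.010 = 1.04. With n per arm, SE = 5 × √(2 × 1.04 / n), and power comes from the noncentral t with participant-level degrees of freedom.
- 30 per arm (6 libraries per arm): 84.8%, which matches 85%.
- 40 per arm: 93.4%; 50 per arm: 97.3%. So 94% corresponds to about 40 per arm, not 50.
- 30 to 50 in total: 54.6% to 77.6%.

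No single reading tried gives both ends of the stated range. That is a separate matter and does not affect the type I error below.

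**2. Type I error of the participant t-test at the plan's inputs.** Ignoring DE makes the test statistic too large by a factor of √DE: 2 × [1 − Φ(1.96 / √1.04)] = 0.0546, about 5.5%. Simulation gives 5.5% for 30 participants in 6 libraries and for 50 in 10.

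**3. The same test with 125 participants.** Over 6 libraries, m = 125/6 = 20.8, DE = 1.198, and the formula gives 7.3%. Over 10, m = 12.5, DE = 1.115, giving 6.3%. At 5 per library there would be 125/5 = 25 libraries, and the figure returns to about 5.5%.

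**4. Does pretest adjustment solve it?** The simulation used normal library and individual effects, with libraries split half and half. Participant-level ANCOVA was run with library effects correlated 0.5 between pretest and posttest, or fully stable. The last column is a t-test on baseline-adjusted library means with (libraries − 2) df.

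| Participants / libraries | ICC | t-test | ANCOVA, library corr. 0.5 | ANCOVA, fully stable | Adjusted library means |
|---|---|---|---|---|---|
| 30 / 6 | 0.010 | 5.5% | 5.5% | 5.2% | 5.0% |
| 50 / 10 | 0.010 | 5.5% | 5.4% | 5.2% | 4.9–5.0% |
| 125 / 6 | 0.010 | 7.4% | 7.3% | 5.8% | 5.0% |
| 125 / 10 | 0.010 | 6.3% | 6.3% | 5.5% | 5.0–5.1% |
| 125 / 6 | 0.05 (assumed) | 17% | 16% | 9% | 5.1–5.2% |
| 125 / 10 | 0.05 (assumed) | 12% | 12% | 7% | 4.8–5.1% |

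If 60 of the 125 come from one library, the t-test error at ICC 0.010 is about 7.7% with 6 libraries and 6.9% with 10; adjusted library means stay at 4.7% to 4.9%. Baseline adjustment therefore removes much of the excess only if library differences persist from pretest to posttest.

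**5. Power of a library-level analysis (4 points, SD 5, ICC 0.010).** With 15 per arm in 6 libraries, SE = 5 × √(2 × 1.04 / 15) = 1.862 and the noncentrality is 4 / 1.862 = 2.148. The critical value is 2.05 on 28 df (power 54.6%) but 2.78 on 4 df (power 37.7%). With 50 participants in 10 libraries the two powers are 77.6% and 68.2%.

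**The case against.** The strongest reply concerns weight. At the plan's own inputs the excess is half a percentage point. The 6% to 7% figures need 125 people in 6 to 10 libraries, a combination the documents do not state. The 12% to 17% figures need an ICC of 0.05, and the 60-person library is an assumption because no attendance figure is given. All of this is right, and those figures are sensitivity results only.

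Second, the remedy costs power, and the fair comparator for a baseline-adjusted library analysis is a baseline-adjusted participant analysis, since the SEM already adjusts for baseline. By noncentral t with the design effect of 1.04 and correlation 0.5, participant-level ANCOVA has about 67% power with 30 people and 88% with 50, against 46% and 79% for adjusted library means. With 6 libraries in total, that is about 20 points of power given up to remove about half a point of type I error. This stands and belongs in the decision. It does not make the participant-level test valid: the low power shows how little information six randomised units carry.

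Third, not stated is not the same as not done. The power sentence links its t-test to clusters and an ICC, and the SEM's covariate list is open-ended. A cluster-adjusted analysis is therefore possible, but the plan does not commit to one.

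Fourth, library may already be on the survey form. That also stands, so the library code is a point to confirm and not a demonstrated gap.

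**Conclusion.** The concern holds. The unit of randomisation is the library, and no efficacy analysis is stated to match it. If the t-test is run as written, its type I error is about 5.5% at the plan's inputs (5 per library, ICC 0.010). It is about 6.3% to 7.4% if 125 people come from 10 or 6 libraries. Larger inflation needs a larger ICC, which the documents do not give. Pretest adjustment at participant level may reduce the excess but does not guarantee 5%. Baseline-adjusted library means held 4.7% to 5.2% in every simulated scenario, including uneven library sizes.

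The error is small on the stated assumptions, but the plan relies on an unsupported ICC and an unstated number of libraries to keep it small. It should be corrected in the analysis plan.

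**What to change.** Name one decisive between-arm analysis for OOKS, and the same for OOAS, that accounts for library with library-level degrees of freedom and adjusts for the pretest score. A simple valid choice is a t-test on library means of baseline-adjusted posttest scores with (libraries − 2) df; another cluster method that is valid with few clusters would also do. State how the SEM accounts for library, or label it supportive. Confirm that each survey carries a library code, and add one if it does not.

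If one library is expected to supply many participants, library means may be weighted using a prespecified ICC. In the uneven case, weighting the unadjusted means at ICC 0.010 raises power from 76%–85% to 80%–91%. Type I error is 4.9% to 5.0% if that ICC is right, but 5.4% to 6.2% if it is really 0.05.

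The direct cost is wording, minor programming and one code. With about 5 people per library, the code together with demographics makes small cells, so it should stay in restricted data. The main cost is power for 4 points at ICC 0.010:

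| Setting | Participant t-test | Library means, unadjusted | Library means, baseline-adjusted (corr. 0.5) |
|---|---|---|---|
| 30–50 in 6–10 libraries in total | 55–78% | 38–68% | 46–79% |
| 6–10 libraries per arm, 5 each | 85–97% | 78–96% | not computed |
| 125 evenly over 6–10 libraries | 98–99% | 86–96% | 93–99% |
| 125, of whom 60 in one library, 6–10 libraries | 97% | 76–85% | 85–93% |
| 125 over 25 libraries | 99% | 99% | not computed |

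In the first row, adjusted library means give 40%–71% at correlation 0.3 and 60%–92% at 0.7. The plan should therefore also state how many libraries will be randomised: recruiting more libraries recovers most of the lost power.

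### The baseline-adjusted comparison that answers the trial's question is planned but not made the decision analysis, while the power statement and the posttest t-test leave the matched pretest unused

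*Combined protocol and SAP*

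**What the plan says.** The Protocol Description gives the aim: "This cluster-randomized trial will compare changes in attitudes and knowledge on administering naloxone". Under Overall objectives, the hypothesis is that VR training "will result in increased knowledge retention and comfort level to administer naloxone". Subject Confidentiality explains why surveys carry an ID number: "Because this study requires measurement of pretest and posttest data, participants data must be matched".

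The Analysis Plan then lists, in this order:

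- between arms, an "independent t-test will assess differences in pre-test knowledge and attitudes prior to intervention between control and experimental groups, and again with a posttest analysis";
- within each arm, "Paired t-test will assess within cohort changes in knowledge and attitudes";
- a power statement for a 4-point difference in mean OOKS, "using a two sided t-test at significance level of 0.05", with SD 5, ICC 0.010, and 30-50 participants in 6-10 libraries averaging 5 each;
- last, "Structural equation modeling will assess differences in control and treatment participants post scores while adjusting for relevant covariates including baseline knowledge and attitudes".

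No analysis is named primary. Only the power statement refers to clustering; none of the listed tests or models says how library enters. The power statement gives no pre-post correlation. It does not say whether the 4 points and the SD of 5 describe post scores or changes, or whether 30-50 is a total or a number per arm.

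**The concern.** The stated question is a between-arm comparison of change. The analysis that most resembles the one powered, an unadjusted posttest t-test, uses no information on change. The tests that address change directly are run within each arm and do not compare the arms. The one planned analysis that is both between-arm and baseline-adjusted has no special standing.

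Two things are at stake.

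- **Precision and chance imbalance.** With few libraries, the arms can differ at pretest by chance. People also join on site, unblinded, at a library whose arm is fixed, so the arms may recruit differently. An unadjusted posttest test carries the correlated part of any pretest difference into the result, and testing the pretest difference does not correct it.
- **Selective emphasis.** The unadjusted, paired and adjusted analyses can disagree, and the plan does not say which one governs. The model's covariates beyond baseline are also left open.

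**Working it through.** **1. The plan's own figure.** Inputs from the Analysis Plan: difference 4, SD 5, two-sided alpha 0.05, ICC 0.010, cluster size 5. The design effect is 1 + (5 - 1) x 0.010 = 1.04. With n per arm, SE = 5 x sqrt(2 x 1.04 / n).

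| Reading | Normal approximation | t, individual df | t, library df |
|---|---|---|---|
| 30 to 50 in total | 57.5% to 79.2% | 54.6% to 77.6% | 37.7% to 68.2% |
| 30 to 50 per arm | 86.0% to 97.5% | 84.8% to 97.3% | 78.2% to 96.0% |

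The stated 85% matches 30 per arm. The stated 94% matches 40 per arm (93.9% normal, 93.4% t), not 50. No single reading gives both ends. That is a separate issue; here it means that the relevant sample size is uncertain, so several are shown below.

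**2. What baseline adjustment gains.** Adjusting for pretest multiplies the variance of the between-arm difference by 1 - r², where r is the pre-post correlation. The documents do not give r, so these are assumed values, applied to the whole variance with the design effect unchanged:

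- r = 0.3: 1 - 0.09 = 0.91, a 9% cut
- r = 0.5: 1 - 0.25 = 0.75, a 25% cut
- r = 0.7: 1 - 0.49 = 0.51, a 49% cut

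Example at 25 per arm, 10 libraries, 10 - 2 = 8 df: unadjusted SE = 5 x sqrt(2.08 / 25) = 1.44, noncentrality 4 / 1.44 = 2.77, power 68%. At r = 0.5 the SE is 1.44 x sqrt(0.75) = 1.25, noncentrality 3.20, power 80%.

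The 125 comes from the number of subjects to be enrolled (Characteristics of the Study Population). Spreading it equally over 10 libraries is my assumption: 12.5 per library, design effect 1 + 11.5 x 0.010 = 1.115, SE = 5 x sqrt(2 x 1.115 / 62.5) = 0.94.

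| Sample, df | Unadjusted | r = 0.3 | r = 0.5 | r = 0.7 |
|---|---|---|---|---|
| 30 total, 6 libraries, 4 df | 38% | 41% | 47% | 62% |
| 50 total, 10 libraries, 8 df | 68% | 72% | 80% | 92% |
| 50 total, individual df | 78% | 81% | 88% | 97% |
| 125 total, 10 libraries, 8 df | 96% | 97% | 99% | above 99% |
| 125 total, individual df | 99% | 99% | above 99% | above 99% |

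A plain between-arm t-test of change scores is not an equivalent remedy. Its SD is 5 x sqrt(2(1 - r)), which is below 5 only if r exceeds 0.5. At 50 total with individual df its power is 63%, 78% and 94% at r = 0.3, 0.5 and 0.7, against 78% for the post score alone.

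**3. Chance imbalance.** If the pretest SD is also 5, the SE of a chance pretest difference is 5 x sqrt(2.08 / 25) = 1.4 points at 25 per arm and 5 x sqrt(2.08 / 15) = 1.9 at 15 per arm, against a 4-point target.

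**4. What the paired tests can show.** Suppose that both arms truly improve equally. If p is the power of one paired test, exactly one arm is significant with probability 2p(1 - p). The SD of change (5) and the true change are assumptions, and clustering is ignored.

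| True change in both arms | 15 per arm | 25 per arm |
|---|---|---|
| 2 points | p = 0.30, 42% | p = 0.48, 50% |
| 4 points | p = 0.82, 29% | p = 0.97, 6% |
| 5 points | p = 0.95, 10% | p = 0.998, 0.5% |

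The 2-point row at 25 per arm is at the maximum of the formula, so it is close to a worst case. These counts include both directions; half of each would appear to favour VR. At 62 per arm a 2-point change gives 22%.

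**The case against.** A reader might infer that the trial has no test of its stated question, because the only tests of change as such are within arm. The Analysis Plan does not support that. The structural equation model compares the arms on post scores and adjusts for baseline knowledge and attitudes. In a linear model that contains the same scale's baseline, the arm coefficient is the same whether the outcome is the post score or the change. With observed scores and one outcome, it is in essence the analysis of covariance recommended below. It follows that no precision is shown to be lost from the plan as a whole; the loss arises only if the posttest t-test decides the trial.

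A reader might also infer that VR will be judged by setting one arm's paired p-value against the other's. The plan never says so. The figures in step 4 show why that inference must not be drawn, not that the sponsor intends it.

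Other parts of the opposing case also stand. Calling the posttest t-test the powered analysis is an inference from the power statement. Sizing a trial on a simple t-test and analysing it with adjustment is common and usually conservative. The precision gain is large only at the smaller sample sizes and higher correlations. Adjustment deals only with imbalance in the measured pretest, not with other differences in who was recruited.

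What the objection leaves untouched is the standing of the model: it is last, unranked, not the basis of the power figure, open in its covariates and silent on library.

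**Conclusion.** The point holds in a limited form. The right kind of analysis is in the plan but is not designated to decide the trial, and the test that the power statement resembles does not use a pretest that every participant is asked to complete.

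The size depends on an unstated correlation and on enrolment. At assumed correlations of 0.3, 0.5 and 0.7, the gain at 50 participants in 10 libraries with 8 df is about 4, 12 and 24 percentage points of power. At 125 participants over an assumed 10 equal libraries it is at most about 4 points. The Study Duration section continues monthly enrolment at one library, so sizes may be unequal, which these figures do not reflect. The lack of ranking among the analyses, and the inability of paired tests to compare arms, hold at any sample size.

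This should be changed, but it is not a fatal flaw.

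**What to change.** In the Analysis Plan:

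- Name as the decision analysis the between-arm difference in posttest OOKS adjusted for the participant's own pretest OOKS. Account for library by a cluster-level analysis or by a random effect with a small-sample correction suited to 6-10 clusters. Do the same for OOAS.
- List in advance any covariates beyond baseline. If the structural equation model is kept, state how it relates to this analysis and how it handles library.
- Keep the unadjusted posttest t-test as supportive only.
- Report within-arm change descriptively with confidence intervals, and state that no VR-versus-standard conclusion rests on it.
- In the power statement, say whether the 4 points and the SD refer to post scores or changes, and give the assumed pre-post correlation with a range.

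The cost is wording: the pretest is already collected and matched. The downside is small. Library-level degrees of freedom make the stated precision somewhat less favourable, for example 68% rather than 78% unadjusted power at 50 participants in 10 libraries.
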